8.6 Stopping Rules for Study Drug

When stopping rules are met for liver chemistry elevations, platelet count reductions, or bleeding events, then Study Drug administration must be discontinued. However, subjects are encouraged to continue with study assessments through the treatment and post-treatment evaluation periods, but will no longer receive Study Drug.

8.6.1 Stopping Rules for Liver Chemistry Elevations

In the event of confirmed laboratory results meeting the following criteria, **and the event is without an alternative explanation as discussed with the Sponsor Medical Monitor (or designee)**, dosing of a patient with Study Drug (ISIS 416858 or placebo) will be stopped permanently; values that are not confirmed due to failure to retest or missing lab values will be presumed confirmed:

1. ALT or AST > 8 x ULN, which is confirmed
2. ALT or AST > 5 x ULN, which is confirmed and persists for 2 weeks
3. ALT or AST > 3 x ULN (or the greater of 2 x baseline value or 3 x ULN if the baseline value was > ULN), which is confirmed and total bilirubin > 2 x ULN or INR > 1.5)

4. ALT or AST $> 3 \times$ ULN (or the greater of $2 \times$ baseline value or $3 \times$ ULN if the baseline value was $>$ ULN), which is confirmed, **and** with the new appearance (i.e., onset coincides with the changes in hepatic enzymes) of fatigue, nausea, vomiting, right upper quadrant pain or tenderness, fever, rash, and/or concomitant eosinophilia ($>$ ULN)

8.6.2 Stopping Rule for Platelet Count Reduction

In the event of a confirmed platelet count less than $75,000/\text{mm}^3$, dosing of a subject with Study Drng (ISIS 416858 or placebo) will be stopped permanently. From the first, additional laboratory investigations will be conducted as outlined in [Table 4](#). The platelet count should be tested weekly until it is above $100,000/\text{mm}^3$. The subsequent follow-up schedule for any events meeting this stopping criterion will be determined by the Investigator in consultation with the Sponsor Medical Monitor (or designee).

In the event of a platelet count $< 50,000/\text{mm}^3$, the Sponsor must be notified within 24 hours and platelets are to be monitored daily until 2 successive values show improvement, then monitored every 2-3 days until the platelet count is stable. A stable platelet count is considered when at least 6 consecutive values measured are $> 100,000/\text{mm}^3$ with no downward trend as determined by the Sponsor Medical Monitor (or designee). It is recommended that the subject receive glucocorticoid therapy to accelerate the recovery in the platelet decline (strongly recommended if platelet count $< 25,000/\text{mm}^3$). To optimize patient treatment, a discussion between the Investigator and the Sponsor Medical Monitor (or designee) must occur. Treatment guidelines for immune thrombocytopenia ([Provan et al. 2010](#)) recommend dexamethasone 40 mg daily for 4 days every 2-4 weeks for 1-4 cycles; prednisolone 0.5-2 mg/kg/day for 2-4 weeks then taper; or methylprednisolone 30 mg/kg/day for 7 days (**note:** may require continuation with oral corticosteroids after methylprednisolone).

8.6.3 Stopping Rule for Bleeding

If an event of Major Bleeding or CRNMB event occurs, the Investigator must notify the Sponsor Medical Monitor (or designee) and the subject should be closely monitored (vital signs, lab tests such as Hb, HCT and platelet count, additional outpatient visits, overnight stays and coagulation tests may be needed) throughout the treatment and during the post-treatment evaluation period.

In the event of Major Bleeding or CRNMB (see definitions in [Section 8.5.3](#)) as assessed by the Investigator, dosing of a subject with Study Drng (ISIS 416858 or placebo) may be stopped permanently. The follow-up schedule for any events meeting this discontinuation criterion will be determined, including the suitability of the subject for resumption of dosing by the Investigator in consultation with the Sponsor Medical Monitor (or designee).

Treatment Precautions:

Recommendations to manage bleeding in a patient will be provided to all study sites:

Specifically, if a patient has Major Bleeding or Clinically Relevant Non-Major Bleeding during the trial, the following measures are to be considered by the Investigators to control that bleeding:

1. Delay of the next injection or discontinuation of treatment in consultation with Sponsor Medical Monitor (or designee) per [Section 8.6.3](#).
2. Review and discontinue concomitant medications that could exacerbate bleeding.
3. Mechanical compression/ Surgical intervention/haemostasis.
4. General volume management: fluid replacement & hemodynamic support.
5. Transfusion (whole blood/packed cells/FFP/platelets).

If bleeding cannot be controlled by these measures, consider administration of one of the following procoagulants (according to the dosages advised in the package insert), FXI concentrate (Hemoleven®), Recombinant Factor Vila (NovoSeven®), or 4-factor concentrate (prothrombin complex concentrate).

ISIS 416858 treatment does not directly inhibit circulating FXI, only production of this clotting factor in the liver. Therefore, the dose of fresh frozen plasma (FFP) or factor concentrate given should aim to increase FXI activity above 0.3 U/mL and should recognize that the half-life of circulating FXI is approximately 50 hours when considering the potential need for re-administration. Additionally, the time necessary to obtain a FXI concentration locally and to infuse FFP should be taken into consideration.

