8.5 Safety Monitoring Rules

Please refer also to the 'Guidance for Investigator' section of the Investigator's Brochure.

Baseline for the routine clinical assessments of chemistry and hematology, PD markers, assessment of clotting, PK assessments, vital signs and ECG for the study will be the last non-missing value prior to the first administration of Study Drug and prior to dialysis on Day 1 ([Appendix A](#)). If Day 1 values are not available, screening values will be used.

For baseline Urea Reduction Ratio determination, the BUN blood collection prior to dialysis as well as the post-dialysis sample on Day 1 will be used.

In addition to the standard monitoring of clinical safety parameters, the following guidelines are provided for the monitoring of selected parameters chosen based on preclinical and clinical observations.

Confirmation Guidance: At any time during the study (Treatment or Post-Treatment Evaluation Periods), any clinical laboratory results meeting the safety monitoring criteria presented below **must be confirmed** by performing measurements (ideally in the same laboratory that performed the initial measurement) on new specimens. All new specimen collections should take place as soon as possible (ideally within 7 days of the initial collection). For stopping rules, if the initial laboratory result is observed during the Treatment Period, the results from the retest **must be available** prior to administering the next dose of Study Drug (ISIS 416858 or placebo).

Re-dosing Guidance: Subjects with initial laboratory test values that reach a stopping rule must not be re-dosed until the re-test results are available. In general, subjects who do not meet the stopping rules based upon retest may continue dosing. However, the Investigator and the Sponsor Medical Monitor (or designee) should confer as to whether additional close monitoring of the subject is appropriate. If any of the stopping criteria described in [Sections 8.6.1, 8.6.2, or 8.6.3](#) are met, the subject will be permanently discontinued from further treatment with Study Drug (ISIS 416858 or placebo), evaluated fully as outlined below and in consultation with the Sponsor Medical Monitor or designee, and will be followed up in accordance with [Section 8.8](#) of the protocol.

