8.7 Discontinuation of Study Drug

A subject must permanently discontinue Study Drug (ISIS 416858 or placebo) for any of the following:

- The subject becomes pregnant. Report the pregnancy according to instructions in [Section 9.5.4](#)
- The subject withdraws consent
- The subject experiences an AE that necessitates permanent discontinuation of Study Drug
- The subject develops laboratory test abnormalities that meet any of the stopping rules listed in [Sections 8.6.1 to 8.6.3](#)
- The subject experiences an AE that necessitates unblinding of the Investigator to the subject's treatment assignment
- The subject is no longer on maintenance hemodialysis of at least 3-times per week for a minimum of 9 hours per week which includes a change in dialysis modality or renal transplantation
- The subject begins treatment with a disallowed concomitant medication as described in [Section 8.9.1](#)

The reason for discontinuation of Study Drug must be recorded in the electronic Case Report Form (eCRF) and source documentation. Every effort should be made to complete the early termination study procedures and observations as detailed in [Appendix A](#) at the time of withdrawal.

Subjects who discontinue Study Drug are encouraged to remain in the study. Subjects that discontinue treatment such as in cases where hemodialysis is held for > 2 weeks or stopped, or there is a change of dialysis modality (i.e., hemodialysis to peritoneal dialysis) or receive a renal transplant (See [Section 6.2.2](#)) are encouraged to complete the treatment and the post-treatment evaluation period visits unless consent is withdrawn.

If the subject declines or is unable to participate in the post-treatment evaluation period, the investigator should clarify what type of follow-up the subject is agreeable to, such as by telephone or through their treating physicians. At the very least, the subject's status at the end of the protocol defined study period should be ascertained and documented wherever possible. The agreed means of follow-up should be documented in the subject's records and notified to the Sponsor.

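### Protocol 8.5 and 8.6 require study drug to stop after a major or clinically relevant non-major bleed, while 8.6.3 only permits stopping and provides for resumption

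*Combined protocol and SAP*

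**What the plan says.** Four protocol sections bear on dosing after MB or CRNMB.

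- **8.5 Safety Monitoring Rules (Re-dosing Guidance)** refers to the criteria in 8.6.1, 8.6.2 or 8.6.3. If any of them "are met, the subject will be permanently discontinued from further treatment with Study Drug".
- **8.6 Stopping Rules for Study Drug** opens: "When stopping rules are met for liver chemistry elevations, platelet count reductions, or bleeding events, then Study Drug administration must be discontinued". Subjects are encouraged to stay for assessments, "but will no longer receive Study Drug".
- **8.6.3 Stopping Rule for Bleeding** takes MB or CRNMB, as assessed by the Investigator, as its trigger and says that dosing "ISIS 416858 or placebo) may be stopped permanently". It adds that the schedule of follow-up for "events meeting this discontinuation criterion will be determined". The same sentence extends that decision to re-dosing, "including the suitability of the subject for resumption of dosing by the Investigator in consultation with the Sponsor Medical Monitor". Among the measures to consider for controlling a bleed it lists "Delay of the next injection or discontinuation of treatment in consultation with Sponsor Medical Monitor (or designee").
- **8.7 Discontinuation of Study Drug** makes permanent discontinuation mandatory where "The subject develops laboratory test abnormalities that meet any of the stopping rules listed in" 8.6.1 to 8.6.3. A separate bullet covers an adverse event that makes permanent discontinuation necessary.

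Protocol 10.1.1 defines the primary safety outcome as the combination of MB and CRNMB during the treatment period.

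**The concern.** The same event receives a mandatory stop in two sections and a discretionary one in the third. In a multicentre trial, two sites could handle identical bleeds in opposite ways, each citing the protocol. CRNMB is a broad category (protocol 8.5.3 includes overt bleeding that led only to a medical examination), and protocol 2.2 describes dialysis patients as being at high risk of bleeding. The instruction is therefore unlikely to be idle.

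The first thing at stake is subject safety and protocol compliance after the trial's key safety event. The second is on-drug exposure after a bleed. That exposure may influence whether a first major bleed follows an earlier CRNMB, and such a bleed would enter the Kaplan-Meier display in SAP 2.3.3.3. It may also decide which subjects and visits reach the analyses that SAP 2.4 runs on the Per Protocol Population.

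**Working it through.** **Comparison of the text**

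| Section | Applies to bleeding? | Consequence | Re-dosing |
|---|---|---|---|
| 8.5 | Yes, cites 8.6.3 | Mandatory, permanent | Excluded |
| 8.6 | Yes, names bleeding events | Mandatory | Excluded |
| 8.6.3 | Yes, it is the bleeding rule | Discretionary | Delay and resumption provided for |
| 8.7 | Cites 8.6.3, but only for laboratory abnormalities | Mandatory | Bleeding case not settled |

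The liver and platelet rules (8.6.1 and 8.6.2) both say that dosing *will* be stopped permanently once their criteria are met. Only the bleeding rule departs from its parent sections. No visible passage states that one section takes precedence over another.

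**Doses at stake per subject**

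The inputs are the 26 weekly doses on Days 1, 8, …, 176 (protocol 6.1.3), so dose k falls on Day 7k − 6. After a bleed following dose k, 8.5 and 8.6 allow 0 further doses and 8.6.3 allows at most 26 − k:

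- k = 1: 26 − 1 = 25
- k = 13: 26 − 13 = 13, half the course
- k = 20: 26 − 20 = 6
- k = 25: 26 − 25 = 1

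**Possible effect on the Per Protocol analyses**

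The Per Protocol definition (SAP 2.1.2) allows at most 2 missed doses in the first 12 weeks and at most 5 over 26 weeks. It does not say whether doses not given after discontinuation count as missed. The two possibilities are alternatives, not cumulative.

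1. *They count as missed.* Exclusion follows if 26 − k > 5, that is k ≤ 20 (k = 20 misses 6, k = 21 misses 5). The 12-week limit, 12 − k > 2, gives k ≤ 9 and adds nothing. A subject stopped at k ≤ 20 leaves the population.
2. *They do not count.* The subject stays in on dose count, but the window for the clotting analysis of category 3 or higher ends seven days after the last dose, on Day (7k − 6) + 7 = 7k + 1. Scheduled clotting visits after Day 50 (SAP visit-window table for clotting) are Days 57, 71, 85, 99, 113, 120, 134, 148, 162 and 176, which is 10 visits.

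| Last dose k | Window ends | Visits kept of 10 |
|---|---|---|
| 7 | Day 50 | 0 (also 0 for any k < 7) |
| 13 | Day 92 | 3 |
| 20 | Day 141 | 7 |
| 21 | Day 148 | 8 |
| 23 | Day 162 | 9 |
| 25 | Day 176 | 10 |

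With k ≤ 7 no scheduled visit falls in the window, so the subject would normally not qualify for that post-Week 8 denominator at all. The per-visit summaries and the comparison at Week 26 or early termination are not stated to be limited by this window.

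These effects follow any permanent stop. They bear on the conflict only for bleeds where the two instructions lead to different dosing.

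**The case against.** The best defence is that 8.5 and 8.6 are conditional: they apply when a stopping rule is met, and 8.6.3 may leave it to the Investigator and Medical Monitor to decide which bleeds meet it. The adverse-event bullet in 8.7 fits this case-by-case reading, since every bleed is an adverse event under 8.5.3. The reading is arguable but does not rescue the text. In 8.6.3 the trigger is the bleed itself, and the sentence on events that meet the criterion is the one that provides for resumption. Resumption after a criterion is met cannot be squared with permanent discontinuation in 8.5 or with no further Study Drug in 8.6. Nor does consultation remove the conflict, because a jointly agreed resumption would still be contrary to 8.5.

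Several objections to the consequences do stand:

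- The 26 − k figures are upper bounds on a hypothetical, not an estimated effect.
- The treatment of doses after discontinuation is a gap in the Per Protocol definition, separate from 8.6.3. Two listed notes to file address that population and cannot be seen.
- The visit counts use nominal days. With the ±3-day dosing window a count can shift by one: dose 21 given on Day 138 closes the window on Day 145, before the Day 148 visit.
- SAP 2.4 also puts the FXI and aPTT analyses on the Per Protocol Population, so clotting is not the only analysis touched.
- The Kaplan-Meier curve is descriptive, with no planned test.
- Subjects are encouraged to remain in follow-up after stopping, so no direct loss of safety data follows.

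**Conclusion.** The contradiction is real and rests on the wording alone. Sections 8.5 and 8.6 exclude dosing after a bleed that meets 8.6.3, while 8.6.3 allows it. The largest difference for one subject is 26 − k doses, from 25 after dose 1 down to 1 after dose 25. The number of subjects cannot be sized, because the documents give neither a bleeding rate for this trial nor the share of bleeds that would be handled differently.

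The incidence of the MB/CRNMB composite is unaffected, since a subject is counted at the first event. Effects on later major bleeds and on the Per Protocol analyses are possible but conditional. They assume the nominal schedule and one of the two readings of missed doses.

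The Medical Monitoring Plan, Safety Management Plan, Investigator's Brochure guidance and notes to file are not visible, and nothing is claimed about their content. This should be fixed because it governs dosing after the primary safety event. No view is taken on which instruction is clinically right.

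**What to change.** Reconcile protocol 8.5, 8.6, 8.6.3 and 8.7 so that they give one consistent instruction on dosing after MB or CRNMB. The sponsor and investigators decide its content and which passages change. Notify sites.

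Optionally, tabulate by arm the action taken with Study Drug after each MB or CRNMB. The adverse event form already collects this (protocol 9.4.3.3), and the SAP partly covers it through the table of events leading to permanent discontinuation and the Bleeding CRF summaries or listings. The table remains possible even if dosing has ended.

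The cost is a wording amendment to a few sections, carried into the Czech and Austrian versions, with regulatory and IRB approval where protocol 12.1 requires it, and a site letter. The optional table needs no new data.

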8.7 Discontinuation of Study Drug

A subject must permanently discontinue Study Drug (ISIS 416858 or placebo) for any of the following:

- The subject becomes pregnant. Report the pregnancy according to instructions in [Section 9.5.4](#)
- The subject withdraws consent
- The subject experiences an AE that necessitates permanent discontinuation of Study Drug
- The subject develops laboratory test abnormalities that meet any of the stopping rules listed in [Sections 8.6.1 to 8.6.3](#)
- The subject experiences an AE that necessitates unblinding of the Investigator to the subject's treatment assignment
- The subject is no longer on maintenance hemodialysis of at least 3-times per week for a minimum of 9 hours per week which includes a change in dialysis modality or renal transplantation
- The subject begins treatment with a disallowed concomitant medication as described in [Section 8.9.1](#)

The reason for discontinuation of Study Drug must be recorded in the electronic Case Report Form (eCRF) and source documentation. Every effort should be made to complete the early termination study procedures and observations as detailed in [Appendix A](#) at the time of withdrawal.

Subjects who discontinue Study Drug are encouraged to remain in the study. Subjects that discontinue treatment such as in cases where hemodialysis is held for > 2 weeks or stopped, or there is a change of dialysis modality (i.e., hemodialysis to peritoneal dialysis) or receive a renal transplant (See [Section 6.2.2](#)) are encouraged to complete the treatment and the post-treatment evaluation period visits unless consent is withdrawn.

If the subject declines or is unable to participate in the post-treatment evaluation period, the investigator should clarify what type of follow-up the subject is agreeable to, such as by telephone or through their treating physicians. At the very least, the subject's status at the end of the protocol defined study period should be ascertained and documented wherever possible. The agreed means of follow-up should be documented in the subject's records and notified to the Sponsor.

8.8 Withdrawal of Subjects from the Study

Subjects must be withdrawn from the study for any of the following:

- Withdrawal of consent
- The subject is unwilling or unable to comply with the protocol

Other reasons for withdrawal of patients from the Study might include:

- At the discretion of the investigator for medical reasons
- At the discretion of the investigator or Sponsor for noncompliance
- Significant protocol deviation

All efforts will be made to complete and report the observations as thoroughly as possible up to the date of withdrawal. All information, including the reason for withdrawal from study, must be recorded in the eCRF. Any subject who withdraws consent to participate in the study will be removed from further treatment and study observation immediately upon the date of request. These subjects should be encouraged to complete the early termination study procedures and observations at the time of withdrawal ([Appendix A](#)).

For subjects withdrawn for reasons other than withdrawal of consent every effort should be made to complete the early termination study procedures and observations at the time of withdrawal (see [Appendix A](#)).

8.9 Concomitant Therapy and Procedures

The use of concomitant therapies or procedures defined below must be recorded on the subject's eCRF. Adverse events related to administration of these therapies or procedures must also be documented on the appropriate eCRF.

8.9.1 Concomitant Therapy

A concomitant therapy is any non-protocol specified drug or substance (including over-the-counter medications, herbal medications and vitamin supplements) administered between the signing of informed consent and the last protocol specified Post-Treatment Evaluation Period visit ([Appendix A](#)).

Allowed Concomitant Therapy

Any medications deemed necessary by the Investigator are allowed except those listed in the disallowed concomitant therapy. The use of stable doses of unfractionated heparin and low-molecular weight heparin during hemodialysis is allowed.

Disallowed Concomitant Therapy

Concomitant use of anticoagulant/antiplatelet agents (e.g., warfarin, dabigatran, rivaroxaban, clopidogrel) that may affect coagulation (except low dose aspirin(;;:100 mg/day) during Treatment and Post-treatment Evaluation Periods is not allowed.

For subjects in the platelet function/activation subgroup, use of any anticoagulants or antiplatelet agents (other than aspirin) is not allowed.

8.9.2 Concomitant Procedures

A concomitant procedure is any therapeutic intervention (e.g., surgery/biopsy, physical therapy) or diagnostic assessment (e.g., blood gas measurement, bacterial cultures) performed between signing of informed consent and last protocol-specified Post-Treatment Evaluation visit ([Appendix A](#)).

8.10 Treatment Compliance

Compliance with Study Drng dosing is to be monitored and recorded in the eCRF by Study Center staff.

9. SERIOUS AND NON-SERIOUS ADVERSE EVENT REPORTING

9.1 Sponsor Review of Safety Information

Safety information will be collected, reviewed, and evaluated by the Sponsor or designee in accordance with the Safety Management Plan and Medical Monitoring Plan throughout the conduct of the clinical trial.

